#### **Figure 2: Accelerated Titration Dose Escalation Schema**

6.2.3 Dose Escalation in Rolling Six Cohorts

Upon completion of a Rolling Six cohort (a minimum of three, maximum of six evaluable patients), if:

• 0 of 3 patients experience a DLT; dose escalation may proceed to the next cohort (no greater than a 50% dose increase)

- 1 of 3 patients experience a DLT; an additional three evaluable patients will be enrolled into the cohort
- $\leq 1$  of 6 patients experience a DLT; dose escalation may proceed to the next cohort (no greater than a 50% dose increase)
- ≥ 2 patients experience a DLT; the MTD has been exceeded and further enrollment into that cohort will cease. Lower-dose cohorts may then be explored until the MTD has been determined, including intermediate doses.

Dose Escalation Schema	Target Dose / Actual Dose	Dose Increase
	60 mg / 60 mg	n/a
All asharts annalled using Assalanted	120 mg / 120 mg	100%
All cohorts enrolled using Accelerated Titration	240 mg / 230 mg	100%
Thaton	460 mg / 460 mg	100%
	920 mg / 920 mg	100%
	60 mg / 60 mg	n/a
Delling six equalles at the sing of the	90 mg / 90 mg	50%
Rolling-six enrollment begins at the 60 mg cohort	135 mg / 120 mg	50%
oo mg conort	180 mg / 180 mg	50%
	270 mg / 260 mg	50%
	60 mg / 60 mg	n/a
Dolling giv angultment begins at the	120 mg / 120 mg	100%
Rolling-six enrollment begins at the 120 mg cohort	180 mg / 180 mg	50%
120 mg conort	270 mg / 260 mg	50%
	390 mg / 380 mg	50%
	60 mg / 60 mg	n/a
Dalling six annullment begins at the	120 mg / 120 mg	100%
Rolling-six enrollment begins at the 230 mg cohort	240 mg / 230 mg	100%
230 mg conort	345 mg / 320 mg	50%
	480 mg / 460 mg	50%
	60 mg / 60 mg	n/a
Dalling six annullment begins at the	120 mg / 120 mg	100%
Rolling-six enrollment begins at the 460 mg cohort	240 mg / 230 mg	100%
	460 mg / 460 mg	100%
	690 mg / 690 mg	50%

## **Table 7: Sample Dose Escalation Tables**

Note: Sample dose levels are based upon dose escalation (target dose) and available VK-2019 capsule strengths of 30 and 200 mg (actual dose).

## 6.2.4 Intra-Patient Dose Escalation in Accelerated Titration Cohorts

After an accelerated titration cohort has been declared safe by the SRC, patients at lower dose levels may be considered for intra-patient dose escalation if they meet the following criteria based in part on 3B design proposed by Simon et al:

- Have stable disease (SD) or better after Cycle 2 (or later)
- Experienced no VK-2019 related Grade 2 AEs during the previous cycle

• Have no other safety concerns as assessed by the investigator

The escalated dose must be agreed upon by the investigator and sponsor and may proceed beginning on Day 0 of the next cycle. Any patient that has their dose escalated will not be evaluated for DLT assessment at their new dose.

#### 6.2.5 Intra-Patient Dose Escalation in Rolling Six Cohorts

After a Rolling Six cohort has enrolled a minimum of three patients and has been declared safe by the SRC, patients at lower dose levels may be considered for intra-patient dose escalation if the patient meets the following criteria:

- Have stable disease (SD) or better after Cycle 2 (or later)
- Have no other safety concerns as assessed by the investigator

The escalated dose must be agreed upon by the investigator and sponsor and may proceed beginning on Day 0 of the next cycle. Any patient that has their dose escalated will not be evaluated for DLT assessment at their new dose.

## **Dose-limiting Toxicity**

DLTs will be determined based on the incidence and intensity of AEs assessed as being at least possibly related to VK-2019 and occurring up to 28 days after initiation of QD VK-2019 dosing on C1D0.

- 6.3.1 Dose-limiting Hematologic Toxicity
  - Grade 4 neutropenia > 7 days
  - Grade 4 thrombocytopenia or Grade 3 thrombocytopenia associated with bleeding or requiring platelet transfusion
  - Grade 3 febrile neutropenia
  - Grade 4 anemia or anemia that requires blood transfusion
- 6.3.2 Dose-limiting Non-hematologic Toxicities

- Any Grade 3 or higher non-hematology toxicity, excluding the following:
  - Toxicities assessed by Investigator as clearly related only to disease progression or intercurrent illness
  - Elevations of AST, ALT, and bilirubin, that correct to Grade 1 within one week and do not meet any of the definitions of acute liver injury as listed below
  - o Other asymptomatic laboratory abnormalities
  - Grade 3 fever without neutropenia that returns to Grade 1 or less within 3 days, and is not associated with hemodynamic compromise (including hypotension, or clinical or laboratory evidence of end organ perfusion impairment)
  - Grade 3 diarrhea, nausea, vomiting, or abdominal pain that returns to Grade 1 or baseline within 3 days and with medical intervention
  - Grade 3 pruritis or rash that returns to Grade 1 or baseline within 7 days or baseline with medical intervention
  - o Grade 3 fatigue
  - Grade 3 tumor flare (defined as pain, irritation or rash that localizes to sites of known or suspected tumor)

A DLT will also include:

- A laboratory finding of acute liver injury defined as:
  - Sustained (> 1 week) doubling of AST or ALT levels to no less than 4 x ULN, or sign of increasing functional liver impairment with > 2x baseline increase in total bilirubin
  - o Increased AST or ALT levels above 8xULN
  - Suspected acute liver injury (per Hy's law) ALT/AST > 3 x ULN in combination with Total Bilirubin > 2 x ULN in the absence of cholestatic injury (ALP < 2 x ULN) and no other cause identified.

- Any AE resulting in a patient missing < 7 days of dosing with VK-2019
- Any AE not otherwise meeting the criteria or timing of a DLT as defined above, but is declared a DLT by the SRC

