	
 
within three days, and is not associated with hemodynamic compromise (including hypotension, or clinical or laboratory evidence of end organ perfusion impairment)
 
o Grade 3 diarrhea, nausea, vomiting, or abdominal pain that returns to Grade 1 or baseline within three days with medical intervention
 

Protocol VK-2019-001	Version 9.0, 15-October-2019
	• Grade 3 pruritis or rash that returns to Grade 1 or baseline within
	seven days or baseline with medical intervention
	• Grade 3 fatigue
	• Grade 3 tumor flare (defined as pain, irritation or rash that
	localizes to sites of known or suspected tumor)
	1 /
	A DLT will also include:
	• A laboratory finding of acute liver injury defined as:
	• Sustained (> 1 week) doubling of AST or ALT levels to no less
	than 4 x ULN, or sign of increasing functional liver impairment
	with $> 2x$ baseline increase in total bilirubin
	
 
Increased AST or ALT levels above 8 x ULN
 

	• Suspected acute liver injury (per Hy's law) $ALT/AST > 3 \times ULN$
	in combination with Total Bilirubin $> 2 \times ULN$ in the absence of
	cholestatic injury (ALP $< 2 \text{ x ULN}$ ).
	• Any AE resulting in a patient missing > 7 days of dosing with VK-
	2019
	• Any AE not otherwise meeting the criteria or timing of a DLT as
	defined above, but is declared a DLT by the SRC
Definition of the	The MTD is defined as the highest dose level of VK-2019 at which
MTD:	fewer than two DLTs are observed in six evaluable patients treated at
	that dose.
Definition of a	A BCAD is defined as a dose level that appears to have preliminary
BCAD:	clinical or biological activity based upon the following criteria:
	• There are no safety concerns in that cohort based upon the SRC's
	analysis of safety data.
	• The following criteria for either clinical or biological activity:
	Clinical:
	• At least one patient has experienced an objective response per
	RECIST v1.1 (i.e., a PR or CR) at that dose level.
	Biological:
	• Post-baseline plasma EBV DNA levels have declined by three
	log from baseline, or are below the lower limit of detection of the
	assay, AND
	• Plasma AUC level VK-2019 at the end of Cycle 1 is above the
	biologically active dose as defined in preclinical models (10,000
Definition of the	ng*h/mL) The dasa of orally administered VK 2010 monotherapy that in the
RP2D	The dose of orally administered VK-2019 monotherapy that, in the
NI 4D	opinion of the SRC, can be safely administered for three or more

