# 9 PATIENT MONITORING, TOXICITY MANAGEMENT, AND DOSE MODIFICATIONS

Each patient will be assessed for the development of any toxicity as outlined in Section 13. Dose adjustments will be made according to the system showing the greatest degree of toxicity. The table below outlines parameters for dose holds, dose reductions, resuming dosing, and study drug discontinuance for AEs assessed to be at least possibly related to VK-2019.

Adverse Event	Action with VK-2019 and Toxicity Management
All Grade 1 AEs	Continue VK-2019 at the same dose level. Manage with supportive therapy at the Investigator's judgment.
All Grade 2 AEs	Continue VK-2019 at the same dose level. Manage with supportive therapy at the Investigator's judgment.
All Grade $\geq$ 3 AEs (unless otherwise noted below)	Hold VK-2019 and administer supportive therapy as required in accordance with local practice/guidelines.
	If AE resolves to Grade $\leq 2$ within 21 days, VK-2019 may be restarted at the same dose (unless meeting criteria for a DLT) or a lower dose pending discussion between the investigator and Sponsor.
	If AE does not resolve to Grade $\leq 2$ after 21 days, permanently discontinue VK-2019 and observe the patient until the AE is resolved.
Grade ≥ 2 diarrhea	Manage with Loperamide (4mg at first onset, followed by 2mg every 2-4 hours (or with each loose bowel movement) until diarrhea free for 12 hours (maximum daily dose: 16 mg/24 hours). If loperamide is ineffective, consider adding Lomotil (5 mg, four times a day), or tincture of opium (15- 20 drops orally every 4 hours), or octreotide (150 to 300 mcg SQ twice daily). Modifications to this regimen can be made per local standard practice.
	Hold VK-2019 and manage as above until resolves to Grade $\leq 2$ .
Grade $\geq$ 3 diarrhea	If diarrhea resolves to Grade $\leq 2$ within 21 days, VK-2019 may be restarted at the same dose (unless meeting criteria for a DLT) or a lower dose pending discussion between the investigator and Sponsor.
	If diarrhea does not resolve to Grade $\leq 2$ after 21 days, permanently discontinue VK-2019 and observe the patient until the AE is resolved.

Adverse Event	Action with VK-2019 and Toxicity Management
Nausea/vomiting, all grades	Standard antiemetics for the treatment of nausea and/or vomiting may be used. If it has been demonstrated that there is significant emetogenic potential based on individual and cumulative AE data, prophylactic anti-emetics may be used using ASCO guidelines.

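### The missed-dose DLT criterion is inverted in protocol 6.3.2: fewer than 7 days there, more than 7 days in the synopsis

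*Protocol*

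**What the plan says.** Protocol 6.3 limits DLTs to AEs at least possibly related to VK-2019 within 28 days of starting daily dosing. Section 6.3.2 then counts "Any Grade 3 or higher non-hematology toxicity, excluding the following". The exclusions include "Grade 3 fatigue" and "Grade 3 diarrhea, nausea, vomiting, or abdominal pain that returns to Grade 1 or baseline within 3 days and with medical intervention".

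Further DLT criteria follow, and the two versions of one of them conflict:

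- Section 6.3.2: "Any AE resulting in a patient missing < 7 days of dosing with VK-2019".
- Synopsis, Definition of DLT: "Any AE resulting in a patient missing > 7 days of dosing".

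Section 9 sets the action for a related Grade 3 or higher AE: "Hold VK-2019 and administer supportive therapy as required in accordance with local practice/guidelines". After recovery to Grade 2 or less within 21 days, "VK-2019 may be restarted at the same dose (unless meeting criteria for a DLT) or a lower dose".

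Under 6.2.1 a patient is evaluable with 75% of Cycle 1 doses received, or with a DLT after at least one dose. The SAP has no DLT definition of its own; SAP 7.14 relies on the protocol's criteria.

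Two other lines are relevant but lesser. The hematologic list in 6.3.1 and the synopsis has "Grade 3 febrile neutropenia" with no mention of higher grades. The bar on intra-patient escalation in accelerated titration cohorts (6.2.4, synopsis, SAP 2.2.4) names related Grade 2 AEs, again without higher grades.

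**The concern.** The two missed-dose rules are opposites, and I find no statement of which takes precedence. The body version has no grade floor: a related Grade 1 AE that costs one dose would be a DLT, while a related AE that costs ten doses would not be one under this clause. It also works against the exclusions in its own section, because Section 9 requires a hold for the Grade 3 events that those exclusions exempt, and a hold costs doses.

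DLT counts decide each Rolling Six step (6.2.3), define the MTD, and are part of the Phase 1 primary endpoint (14.1.1). In an accelerated titration cohort a single DLT adds five patients at that dose (6.2.2). For the individual patient, a DLT is a listed reason to stop treatment (Patient Withdrawal) and removes the option of a same-dose restart in Section 9.

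**Working it through.** The plan states no figure for this clause, so there is none to reproduce. The check is how each wording classifies the same patient.

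**Inputs.** 28-day cycles and once-daily dosing (protocol Sections 4 and 6.2), so 28 Cycle 1 doses and one dose per missed day. The evaluability threshold is 75% (6.2.1), read as at least 75%: 0.75 × 28 = 21 doses. Assume a related AE, no other DLT criterion met, no DLT declaration by the Safety Review Committee (SRC), and all missed doses falling in Cycle 1.

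**Formula.** Share received = (28 − doses missed)/28.

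| Doses missed | Share received | By 6.3.2 (fewer than 7) | By synopsis (more than 7) |
|---|---|---|---|
| 1 to 6 | 27/28 = 96.4% to 22/28 = 78.6% | DLT | Evaluable, no DLT |
| 7 | 21/28 = 75.0% | Evaluable, no DLT | Evaluable, no DLT |
| 8 or more | 20/28 = 71.4% or less | No DLT and not evaluable | DLT, so evaluable |

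The synopsis wording meets the 75% rule exactly. Seven missed doses leave the patient evaluable; from the eighth, the AE is a DLT and the patient still counts. Under 6.3.2 that patient leaves the count.

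**One patient.** Related Grade 3 fatigue is exempt in 6.3.2 and held under Section 9.

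- Held 3 days (25/28 = 89.3%): DLT by 6.3.2, no DLT by the synopsis.
- Held 10 days (18/28 = 64.3%): by 6.3.2 neither a DLT nor evaluable; DLT by the synopsis.

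**One cohort.** Two of six patients are each held 3 days and there is no other DLT. By 6.3.2 the count is 2/6, so the dose is above the MTD. By the synopsis it is 0/6, so escalation may proceed.

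**Sensitivity, on assumed rates.** Let p = 18% be the DLT rate from all other criteria (the ceiling in the Phase 1 hypothesis). Let q be the share of patients with a related AE that costs one to six doses, assumed independent and varied from 5% to 30%. The documents give no q. The rate counted under 6.3.2 is t = 1 − (1 − p)(1 − q):

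- q = 5%: t = 1 − 0.82 × 0.95 = 22.1%.
- q = 30%: t = 1 − 0.82 × 0.70 = 42.6%.

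The chance of escalating by 0/3, or by 1/3 then 0/3, is (1 − t)³ + 3t(1 − t)² × (1 − t)³. It is 0.752 at 18%, 0.663 at 22.1% and 0.269 at 42.6%. The chance of fewer than two DLTs in six, (1 − t)⁶ + 6t(1 − t)⁵, is 0.704, 0.604 and 0.195. These figures show direction and possible range only. They omit the patients with eight or more missed doses whom 6.3.2 drops, which works the other way.

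**The case against.** The best reply is that the 6.3.2 wording is plainly a slip. No committee would call one missed day dose-limiting and eight not, the synopsis has the sensible version, and the SRC reviews every cohort before the next dose. The SAP serves an abbreviated CSR and reports that no biopsies were collected (SAP 7.12), so conduct may be largely over. Much of this stands: the 2/6 against 0/6 example shows what the text permits, not what happened. But the protection runs one way. The DLT section lets the SRC add a DLT; I find no clause that lets it remove one created by the body wording. And SAP 7.14 takes its DLTs from the protocol, so the conflict reaches the report.

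A reader might infer more: that three safety thresholds are wrong, with Grade 4 febrile neutropenia outside the DLT list and a patient with a recent Grade 3 AE free to escalate. The documents do not support that. The hematologic list uses bare grades elsewhere too, for anemia and thrombocytopenia, and a minimum grade is the natural reading. Both wordings are the same wherever they appear. For febrile neutropenia, the SRC can declare a DLT. For intra-patient escalation, 6.2.4 also requires that the investigator have no other safety concerns and that investigator and sponsor agree the dose; the Rolling Six counterpart (6.2.5) has no grade bar at all and relies on the same judgement. These safeguards are discretionary, which justifies a clarifying edit but not a finding of equal weight.

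**Conclusion.** The missed-dose criterion is contradictory, and the body version is almost certainly the wrong one. It defeats exclusions in its own section, and only the synopsis wording fits the 75% rule. The two wordings classify a related AE differently at every number of missed Cycle 1 doses except seven, provided no other DLT criterion applies. That is enough to reverse a cohort decision (2/6 against 0/6). The result assumes 28 daily doses and an inclusive 75% threshold.

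A reader might infer that the MTD or an escalation step was actually set wrongly. The documents do not show that: they give no event rates and do not say which wording was applied. The point should be fixed because a primary safety count depends on it and the correction is small.

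**What to change.** - **Protocol 6.3.2:** change the criterion to more than 7 days, matching the synopsis. SAP 7.14 then follows without further change.
- **If escalation is complete and the protocol will not be amended:** state in SAP 7.14 that more than 7 days applies. In the first-cycle DLT listing (SAP 7.14.1), mark any DLT counted only because one to six doses were missed. In the general AE listing, flag any related first-cycle AE with more than 7 days of missed dosing that was not counted as a DLT. The flag belongs there because such events are not rows in the DLT listing.
- **Clarifying edits at the same time:** febrile neutropenia of Grade 3 or higher in 6.3.1 and the synopsis; no related AE of Grade 2 or higher in 6.2.4, the synopsis and SAP 2.2.4.

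The cost is a few words, or two listing flags with some derivation of missed days attributable to AEs. A DLT count may change slightly in either direction, and a few patients may lose eligibility for intra-patient escalation.

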## **Dose Escalation Procedures**

The starting dose for VK-2019 is 60 mg QD. Sample dose escalation tables are below in Table 7, detailing a sample dose escalation schema based upon when escalation converts from Accelerated Titration to a Rolling Six design.

6.2.1 Definition of a Completed Cohort and an Evaluable Patient Each dose escalation cohort will consist of either:

- 1 evaluable patient (Accelerated Titration cohorts), or
- 3-6 evaluable patients (Rolling Six cohorts)

[figure not shown]
To be considered evaluable, a patient will have and one of the following:

- Received 75% of doses during Cycle 1, or,
- Received at least one dose of VK-2019 and experienced a DLT during Cycle 1
- 6.2.2 Dose Escalation in Accelerated Titration Cohorts

Upon completion of an accelerated titration cohort (Figure 2),

- IF: No VK-2019 related Grade ≥ 2 AEs occur during Cycle 1; THEN: Dose escalation may proceed to the next accelerated titration cohort (no greater than a 100% dose increase).
- IF: The patient experiences any VK-2019 related Grade ≥ 2 AE during Cycle 1 (not meeting the definition of a DLT); THEN: Convert the current cohort to the Rolling Six design and enroll an additional 2-5 patients (3-6 total).
- IF: The patient experiences a DLT; THEN: Convert to the Rolling Six design and enroll an additional five patients (six total).

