#### **Definition of the MTD**

The MTD is defined as the highest dose level of VK-2019 at which fewer than two DLTs are observed in six evaluable dose escalation patients at that dose level.

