## Patient Withdrawal

Patients may withdraw from the trial at any time at their own request, or they may be withdrawn at any time at the discretion of the investigator or sponsor for safety, behavioral, or administrative reasons. Patients that withdraw from treatment should be encouraged to return for the end-of-treatment visit, complete all safety assessments, and enter long-term follow-up. If the patient withdraws from both treatment and follow-up, no further evaluations should be performed, and no additional data should be collected. The Sponsor may retain and continue to use any data collected before such withdrawal of consent.

The primary reason for withdrawal must be recorded in the subject's medical record and in the appropriate eCRF pages. If a subject is withdrawn for more than one reason, each reason should be documented in the source document and the most medically significant reason should be entered on the eCRF. For example, in order to best characterize the safety profile of VK-2019, patients that withdraw consent from treatment due to tolerability issues with VK-2019 should be captured in the eCRFs as having discontinued due to AE or toxicity instead of having withdrawn consent from treatment.

Patients will be discontinued from treatment and begin long-term follow-up in the case of:

- Disease progression or requirement for anticancer therapy not specified in the protocol.
- Inter-current illness, general, or specific changes in the patient's condition where, in the opinion of the Investigator, further treatment is not in the best interest of the patient.
- DLT or unmanageable AE related to therapy.
- Withdraw of consent from treatment.
- Significant protocol violation or non-compliance with protocol.
- Termination of the study by Sponsor. Note: Any patients still receiving investigational product at the time of study termination by the sponsor will be able to continue to receive VK-2019 if they are deriving clinical benefit and after agreement between the Investigator and sponsor. Such patients will continue to be monitored for SAEs as

described in Section 13. Drug Accountability information must still be collected until all patients have completed treatment.

Patients will be withdrawn from study (long-term follow-up) in the case of:

- Withdrawal of consent from follow-up.
- Patient lost to follow-up.
- Death.
- Termination of study by Sponsor.

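### Section 6.3.2 prints the missed-dose DLT criterion as fewer than 7 days, the reverse of the synopsis; it should read more than 7 days

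*Protocol*

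**What the plan says.** Both DLT definitions cover AEs at least possibly related to VK-2019 that occur within 28 days of starting daily dosing, and both end with a list of additional events that count. On interruptions of dosing they disagree:

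- Synopsis, Definition of DLT: "Any AE resulting in a patient missing > 7 days of dosing".
- Section 6.3.2: "Any AE resulting in a patient missing < 7 days of dosing with VK-2019".

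The SAP reprints the escalation rules but not the DLT definition. Its Section 7.14 refers to the criteria defined in the protocol, and Section 7.14.1 promises a first-cycle DLT summary and listing. Neither document says whether the synopsis or the body prevails.

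The rules that depend on this criterion, or bear on how to read it, are:

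- Evaluability (Section 6.2.1): "Received 75% of doses during Cycle 1", or at least one dose and a DLT in Cycle 1.
- Exclusions from DLT (Section 6.3.2): among others, "Grade 3 diarrhea, nausea, vomiting, or abdominal pain that returns to Grade 1 or baseline within 3 days" with medical intervention.
- Committee discretion (Section 6.3.2): an AE that meets no listed criterion may still count if it falls outside the list "but is declared a DLT by the SRC".
- MTD: the highest dose at which "fewer than two DLTs are observed in six evaluable dose escalation patients".
- Restart (Section 9): after a hold, dosing may be "restarted at the same dose (unless meeting criteria for a DLT".
- Patient Withdrawal: reasons to stop treatment include "DLT or unmanageable AE related to therapy".

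**The concern.** The body section that defines DLTs states one criterion backwards. Taken literally, a related AE that costs one dose is a DLT, while one that costs two or three weeks of dosing is not, at least by this bullet. The bullet has no grade floor, so even a related Grade 1 or 2 AE with a single missed dose would count.

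DLT counts drive the Rolling Six decision (Section 6.2.3) and the MTD. A DLT in an accelerated-titration patient commits that cohort to six patients (Section 6.2.2). DLTs are also part of the Phase 1 primary endpoint (Section 14.1.1). They are not the only input: accelerated titration converts on any related Grade 2 or higher AE, and the Safety Review Committee (SRC) also weighs PK and other data.

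The committee's discretion protects in one direction only. It can add a DLT that the literal text misses, but Section 6.3.2 gives it no power to remove an event that meets a listed criterion. Over-counting of short holds therefore has no stated remedy.

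**Working it through.** No sample size, power or error rate in the plan depends on this bullet, so there is no stated figure to reproduce. The check has two parts: which sign fits the rest of the protocol, and how much the choice could matter.

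**Which sign is intended**

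1. *Exclusions.* Section 6.3.2 excludes Grade 3 gastrointestinal events and fever that settle within 3 days, and rash or pruritus that settles within 7. Section 9 generally requires a hold for related Grade 3 or higher AEs, and specifically for diarrhea, nausea and vomiting. Under fewer than 7 days, a hold of 1 to 6 days would turn an excluded event back into a DLT, so the time-limited exclusions would have little left to do. Under more than 7 days they work.
2. *Restart.* Section 9 allows up to 21 days for resolution and then a same-dose restart unless the event is a DLT; a DLT is also a reason to stop treatment. Under fewer than 7 days, a one-day hold triggers both consequences and, by this bullet, a hold of 8 to 21 days triggers neither.
3. *Evaluability.* 0.75 × 28 = 21 doses, so 7 may be missed. Eight missed doses leave 20/28 = 71.4%. Under more than 7 days the rules meet: up to 7 missed is evaluable on doses, and 8 or more missed in Cycle 1 for a related AE is evaluable through the DLT. Under fewer than 7 days, the patient missing 8 or more is neither a DLT by this bullet nor evaluable, unless another criterion or the SRC intervenes.

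**How much it could matter**

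The documents give no event rates, so these are assumptions: b = 0.10, the DLT rate from all other criteria; L, the share missing more than 7 days for a related AE; S, the share missing 1 to 6 days. Missed doses are taken as independent of b. A cohort clears with 0 of 3, or with 1 of 3 and then 0 of the next 3:

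P(fails to clear) = 1 − [(1−p)³ + 3p(1−p)⁵]

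- Synopsis: p = 1 − (1−b)(1−L)
- Section 6.3.2: p = 1 − (1−b)(1−S)
- Section 6.3.2 with non-evaluable patients replaced: p = [1 − (1−b)(1−S)] / [1 − (1−b)L]

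First row as an example: synopsis p = 1 − 0.90 × 0.95 = 0.145, so P = 0.176. Section 6.3.2 p = 1 − 0.90 × 0.80 = 0.280, so P = 0.464. With replacement, p = 0.280/0.955 = 0.293, so P = 0.492.

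| L | S | Synopsis p → P | Section 6.3.2 p → P | Section 6.3.2 with replacement p → P |
|---|---|---|---|---|
| 0.05 | 0.20 | 0.145 → 0.176 | 0.280 → 0.464 | 0.293 → 0.492 |
| 0.05 | 0.10 | 0.145 → 0.176 | 0.190 → 0.270 | 0.199 → 0.289 |
| 0.05 | 0.05 | 0.145 → 0.176 | 0.145 → 0.176 | 0.152 → 0.190 |
| 0.10 | 0.05 | 0.190 → 0.270 | 0.145 → 0.176 | 0.159 → 0.205 |

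Section 6.3.2 is the stricter text in the first two rows and the laxer in the last. In the third row, before replacement, the probabilities agree but different patients are counted.

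**The case against.** The best reply is that this is a one-character misprint with an obvious correct reading. The literal text is absurd, the right text is in the synopsis, and DLT calls pass through a committee with two external oncologists. Nothing shows that anyone applied the wrong sign. The SAP serves an abbreviated study report (SAP Section 1) and says that no biopsies were collected (SAP Section 7.12), so escalation decisions have probably been taken already. A precedence rule could also sit in the SRC Charter, which is not among the documents reviewed. All of this bears on how likely harm was. It does not make the operative definition correct, and the DLT summary and listing still need a single criterion.

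Three narrower points stand:

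- *Overlap.* The independence assumption is doubtful, because Grade 3 or higher AEs trigger both holds and other DLTs. Suppose short holds overlap the 10% base as fully as possible and long holds are separate. Then L = 0.05, S = 0.20 gives p = 0.15 against 0.20, and P = 0.19 against 0.29. With S = 0.10, p = 0.15 against 0.10, and P = 0.19 against 0.09, so the direction reverses. The formula also leaves out cohorts that go straight to six patients after a DLT in accelerated titration.
- *Fatigue.* The Grade 3 fatigue exclusion has no time limit, so a hold of 8 or more days would override it under the synopsis wording too. It does not help to choose between the signs; the time-limited exclusions do.
- *Cycle boundary.* The DLT window limits when the AE occurs, not when doses are missed. An AE that costs the last 4 doses of Cycle 1 and the first 5 of Cycle 2 leaves 24/28 = 86% of Cycle 1 doses, yet 9 days are missed. The exact fit with the 75% rule holds only for interruptions wholly within Cycle 1.

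**Conclusion.** The concern holds. The two texts cannot both apply, and the synopsis version is the one that fits the rest of the protocol. That more than 7 days was intended is an inference, since no sentence says so, but the synopsis, the time-limited exclusions, the hold and restart rules and the evaluability threshold all agree.

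The size of the effect is uncertain in both magnitude and direction. Across the assumed rates, the chance that a cohort fails to clear moves from 0.18 to 0.46 at one end and from 0.27 to 0.18 at the other, and overlap between causes can shrink or reverse the difference. The conclusion does not rest on these figures. It rests on an operative safety rule, behind escalation, the MTD and a primary endpoint, being wrong as written. That makes it a must-fix despite the small edit.

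**What to change.** Change the sign in Section 6.3.2 to more than 7 days, by clarification letter or in the next amendment. Exactly 7 missed Cycle 1 doses then leaves a patient evaluable (21/28 = 75%) and not a DLT by this criterion.

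Because the trial appears to be at the reporting stage, also:

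- state in the SAP or study report which criterion the SRC applied;
- before the DLT summary and listing are final, recheck every dosing interruption caused by a related AE with onset in the DLT window against more than 7 days, following the interruption into Cycle 2 where it runs on.

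The cost is one character, one sentence and a review of dosing records. No extra patients are needed.
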